1.2 Independent Safety Monitoring Committee

Safety of the study will be monitored on an ongoing basis by an independent data, safety monitoring board (DSMB) consisting of two senior Neonatologists, a biostatistician, and a pediatric pulmonologist with significant experience in multicenter clinical trials. The DSMB will promptly receive information on all adverse experiences and will have final authority to terminate enrollment in the study if deemed necessary (see stopping rules). The randomization code for the study will be provided to the DSMB if requested; otherwise the DSMB will remain blinded.

2 BACKGROUND INFORMATION

2.1 Indication to be Studied

The purpose of the present study is to evaluate the efficacy of a single intratracheal (IT) dose of rhCC10 to intubated premature infants receiving positive pressure ventilation for treatment of respiratory distress syndrome (RDS) to prevent long term respiratory complications referred to as chronic respiratory morbidity (CRM; asthma, cough, wheezing, multiple respiratory infections). Traditionally, short term predictors of CRM have involved the diagnosis of bronchopulmonary dysplasia (BPD). However, the clinical definition of BPD has changed several times over the past decade. The current consensus method for determining BPD is assessing oxygen requirements at 36 weeks corrected gestational age (CGA) using a target oxygen saturation range of 88-94% or through oxygen

challenge testing. However a cohort of premature infants followed to 18-22 months CGA demonstrated that this definition correctly predicted CRM only 35-40% of the time, although accuracy increased as the severity of BPD worsened. A major problem for investigators studying BPD is that premature infants who do not develop BPD can also suffer CRM and have lung function abnormalities at follow-up. In view of these significant methodologic difficulties, the American Academy of Pediatrics, the NIH and FDA have recommended that clinical trials should evaluate CRM in the first 1-2 years of life as a potentially more meaningful outcome.

Extremely low gestational age infants (ELGANs) with RDS are at particular risk of developing BPD, a condition associated with marked inflammation, injury to small airways, and arrest of alveolarization that is believed to result in CRM. BPD is associated with significant morbidity (asthma, repeated pulmonary infections, re-hospitalizations) and mortality, and affects up to 15,000 infants in the US annually. The lungs of premature infants are deficient in factors that regulate inflammatory responses (including CC10). This is critically important since intrauterine infection and inflammation are believed to be involved in the pathogenesis of preterm delivery as well as acute and chronic lung injury. These factors are normally present in the term lung in preparation for the transition to the extrauterine environment. RDS and the associated immature lung structure require rescue with exogenous surfactant and support with supplemental oxygen and positive pressure mechanical ventilation, which amplifies lung inflammation, injury, fibrosis, and impaired lung development.

2.2 Study Drug

The study drug, rhCC10, is a recombinant version of natural human CC10 protein. Native CC10 is produced primarily by non-ciliated respiratory epithelial cells, called Club (Clara) cells and is the most abundant protein in the mucosal fluids in normal healthy lungs. CC10 circulates in the blood and is excreted in the urine. The recombinant version is nearly identical to the native protein and shares all biological properties with the native protein that have been characterized thus far. rhCC10 is produced in *E. coli* bacteria.

The rhCC10 drug formulation to be used in this study is a clear, colorless liquid formulated in unbuffered normal saline (0.9%) at a concentration of 5.5 mg/ml. It is aliquoted into sterile septum-capped, 2 ml glass vials and stored at 4°C. rhCC10 is stable under these conditions for at least 14 years and stable at room temperature for at least 18 months. This formulation has been administered by IT instillation in premature infants and by intranasal instillation in healthy adults.

Drug administration: In the previous pilot clinical trial in premature infants, a single dose (1.5 and 5 mg/kg/dose) of rhCC10 was administered by IT instillation within 24 hours of birth in intubated premature infants treated for surfactant deficiency. In the present study, administration of rhCC10 will

be nearly identical to the first clinical trial, however, in the present study the administration of study medication to each lung will be specifically instilled over not less than a 30 second period (duration of instillation not specified in first trial). In addition, just prior to instillation, adjust ventilator settings as follows:

- Increase PIP by 1-2 cm H₂O
- Increase the rate to 35 (if not already there)
- Increase FiO₂ by 5-10%

Dose selection: The IT dose will replicate the single IT doses of 1.5 mg/kg and 5.0 mg/kg from the previous clinical study. Doses will be calculated based on the patient's birth weight.)

2.3 Rationale for the Clinical Study

BPD is a disorder characterized by marked inflammation and alveolar hypoplasia, affecting 20-60% of extremely low birth weight preterm infants. It is associated with significant mortality and short- and long-term morbidity. Long-term morbidities include CRM such as asthma and repeated respiratory tract infections during infancy that lead to increased hospitalizations and treatments with asthma medications. Abnormal neurodevelopmental outcomes, retinopathy of prematurity (ROP), and other significant morbidities of prematurity occur at increased frequency in infants with BPD. While exogenous surfactant therapy has reduced the overall severity of BPD, the prevalence of BPD has increased with improved survival of these infants. New treatments to prevent BPD and subsequent CRM are urgently needed.

There is ample rationale for studying CC10 supplementation in these patients. The phenotypes of two different strains of CC10 knockout mice indicate that CC10 is an autocrine factor required for the normal development of non-ciliated airway epithelial cells, including Club (Clara) cells. CC10 regulates inflammatory responses and protects the structural integrity of pulmonary tissue while preserving pulmonary mechanical function during various insults (e.g. viral infection, bacterial endotoxin, ozone, allergens, hyperoxia). Together these properties suggest that administration of rhCC10 may help to facilitate development of normal airway epithelia and prevent the inflammation that leads to CRM in these infants.

2.4 Non-Clinical Studies: Pharmacology and Toxicology Studies

Native CC10 is produced primarily by non-ciliated respiratory epithelial cells and is the most abundant protein in normal adult lungs, constituting up to 7% of the total extracellular protein. Native CC10 is synthesized by a number of tissues including the lungs, pancreas, uterine endometrium, prostate, and seminal vesicles. The normal physiological tissue distribution for CC10 includes all

mucosal tissues except the eyes and central nervous system. The concentration of endogenous CC10 in the blood ranges from 10-120 ng/ml in normal, healthy adults and up to 5 µg/ml in patients with renal dysfunction. From the blood, CC10 enters numerous tissues and organs and is also excreted in the urine. Several studies have found significantly lower endogenous CC10 protein concentration and expression in the lungs of preterm infants who died or developed severe BPD, suggesting an integral role of this protein in normal lung homeostasis.

The CC10 protein has potent anti-inflammatory and anti-fibrotic properties as demonstrated by numerous *in vitro* and *in vivo* studies. Although there is no consensus as to the central mechanism of action, CC10 may mediate many of its short term anti-inflammatory effects through its role in vesicle and protein trafficking in Club (Clara) cells. Respiratory epithelial cells in CC10 knockout mice demonstrate a lack of secretory vesicles and the presence of unusual intracellular structures characterized by multi-layer stacked membranes and disproportionate amounts of Golgi, rough endoplasmic reticulum, and lysosomal compartments compared to respiratory epithelial cells from non-knockout mice. In the longer term, CC10 may mediate effects through development and/or maintenance of airway epithelial cells, including Club (Clara) cells (autocrine function), which secrete the majority of native CC10 in the lungs and circulation.

rhCC10 follows the natural physiological distribution path for the native protein from lung to blood and blood to urine. The circulating half-life of rhCC10 is 2-2.5 hours, which is prolonged to 9-11 hours by an uptake phase when administered to a mucosal surface (intratracheal instillation). The circulating half-life decreases slightly with increasing dose, suggesting active clearance of the protein. Although all tissues and organs are exposed to CC10, tissues that primarily take up excess rhCC10 include the lungs (airways and alveoli), esophagus, and thyroid. Not only is excess circulating rhCC10 taken up specifically by the lungs, but also small amounts of protein actually reach the extracellular mucosal fluid where it is detected in tracheal aspirate fluid (TAF) and bronchoalveolar lavage fluid (BAL).

Several toxicology studies have been conducted with no evidence of acute or chronic toxicity or any significant tissue pathology, including IT administration in newborn piglets (n=86), premature lambs (n=22), premature baboons (n=4), and juvenile rabbits (n=18). No evidence of acute or chronic toxicity was observed in adult cynomolgus monkeys that received seven daily intranasal doses of rhCC10. No evidence of acute or chronic toxicity was observed in juvenile rats that received 14 daily IV doses of rhCC10. Several models of acute lung injury and infection (RSV, influenza) have demonstrated the protective effects of rhCC10 (by different routes of administration) without evidence of toxicity.

The second trial was performed in healthy adults with seasonal allergies in which rhCC10 was administered by intranasal instillation (1.1 mg per day for seven consecutive days). The study was a placebo-controlled, double-blinded, cross-over design at a single center in Sweden. Patients were previously characterized with allergies to tree pollen but were otherwise healthy. Each subject was given a daily intranasal instillation of rhCC10 immediately prior to receiving an intranasal instillation of allergen. This nasal allergen challenge (NAC) causes a mild inflammatory response in the nasal epithelia. Total nasal symptoms scores (TNSS) were documented within 30 minutes of each challenge. Repeat intranasal administration of rhCC10 did not affect TNSS in this model, but also raised no safety or tolerability concerns. No blood was taken in this study and it is not clear whether intranasal dosing resulted in systemic exposure.

2.5.2 Non-Therapeutic Studies of Human CC10 Physiology

Several studies have examined the concentrations of endogenous CC10 in premature newborn infants and found that CC10 concentration in pulmonary fluids is directly proportional to gestational age. A variety of methods have been used to detect and measure native CC10 in these studies including radioimmunoassay, ELISA, and LC-mass spectrometry. The consensus findings are that pulmonary CC10 expression and protein levels in lung fluids are low in ELGANS and increase over time with increasing gestational age. Rapid increases in CC10 levels in TAF occur following premature birth. No studies have been performed to document CC10 TAF levels in term infants with normal lungs. One study documented that CC10 mRNA is detectable in human fetal lungs as early as week 16, with the protein becoming detectable in amniotic fluid around week 22, and rapidly increasing after week 28 then plateauing at week 32 (~ 1 µg/ml; a pattern similar to surfactant proteins). Another study showed that CC10 levels are lowest in preterm infants who die or develop BPD compared to those who do not, and that a greater proportion of the native CC10 in patients who die or develop BPD is oxidized. It is notable that CC10 is also produced by the uterine endometrium and the placenta during the first and second trimesters of pregnancy, such that the fetus is exposed to CC10 throughout pregnancy and before the fetal lungs start producing it.

2.6 Potential Risks

Human CC10 is a natural product of respiratory epithelia and is normally present in the extracellular fluid of the lung, as well as amniotic fluid. The clinical protocol proposes to supplement low endogenous CC10 levels in the lungs of premature neonates with a recombinant human protein. Thus, we do not expect immunogenicity to be a problem. Peak concentrations of rhCC10 in lung fluid and blood of infants to be treated may exceed normal adult levels, but should be well within the ranges explored in non-clinical pharmacology and toxicology studies. rhCC10 has been tested in non-clinical toxicology studies at doses up to 25 mg/kg (IT) and 2 mg/kg (IV).

CC10 is transcriptionally upregulated in the lungs by corticosteroids. Therefore, patterns of toxicity secondary to excessive CC10 that could occur secondary to treatment with corticosteroids were specifically examined in the first study in preterm infants and in all animal pharm/tox studies. Although no such toxicities have been detected, these effects will continue to be monitored closely in the present studies.

The pharmacokinetic analysis of CC10 in TAF fluids in the first trial demonstrated a trend that native CC10 expression was higher in day 3 TAF of placebo infants than in CC10-treated infants. Although the number of day 3 TAF samples was extremely limited (n=2-3/group due to many infants

being extubated), there is a possibility that administration of exogenous rhCC10 may transiently suppress expression of the native protein in the lungs. This will be closely monitored during the present trial.

There was a higher incidence of confirmed (n=3) and suspected (e.g. radiologic; n=5) NEC in rhCC10-treated infants compared to the placebo group (P=NS). This was not thought to be due to administration of study drug, since the NEC occurred 3-6 weeks after rhCC10 administration and because other infants in the NICU who were not enrolled in the study also developed NEC at the same time. (NEC is known to occur in clusters). However, the incidence and severity of NEC, as well as other infectious related AEs (e.g. sepsis, pneumonia, etc.) will be closely monitored during this study.

3 OBJECTIVES OF THE STUDY

The purpose of the placebo-controlled study is to determine the efficacy of a single IT dose of rhCC10 (1.5 and 5 mg/kg in a 2 ml/kg fixed volume) in improving survival without CRM as indicated by a reduction in respiratory complications 12 months CGA (using validated respiratory diaries and pulmonary questionnaires, see Appendices D, E, and F). Based on these data, future studies will be designed to determine whether administration of rhCC10 to neonates with RDS is effective in improving survival without CRM.

4 STUDY DESIGN

This study is designed as a randomized, blinded, placebo-controlled phase 2 trial. The study will enroll premature infants with a gestational age of 24-29 weeks who are receiving positive pressure mechanical ventilation and surfactant replacement therapy for treatment of RDS. Placebo (normal saline) will be compared to two dose groups of rhCC10 as shown in Table 1:

TABLE 1: TREATMENT GROUPS FOR IT RHCC10 ADMINISTRATION

| Treatment | Route of Administration | Number of doses | Intratracheal Dose level |
|------------------|-------------------------|--------------------|--------------------------|
| Placebo (n = 44) | Intratracheal | 1, on day of birth | n/a |
| rhCC10 (n = 22) | Intratracheal | 1, on day of birth | 1.5 mg/kg |
| rhCC10 (n = 22) | Intratracheal | 1, on day of birth | 5 mg/kg |

The clinical study has a blinded, placebo-controlled design. The purpose of blinding the study is to minimize treatment bias while randomization offers each infant the possibility of receiving the study drug.

A total of 88 patients will be enrolled in three treatment groups in which high and low dose rhCC10 will be compared to placebo. A total of 44 patients will receive placebo, 22 patients will receive 1.5 mg/kg rhCC10, and 22 patients will receive 5 mg/kg rhCC10. Complete results of the study should allow direct comparison of three groups.

Patients enrolled in the study will meet the prescribing criteria for *Survanta* or *Curosurf* and will receive the usual recommended clinical dose of surfactant replacement therapy. Each patient will then receive a single IT dose of the study drug (or placebo) within four hours after surfactant. Patients may be given subsequent doses of surfactant if required, but will not receive additional doses of rhCC10.

Concentrations of rhCC10 will be evaluated in serum derived from the infant, umbilical cord, or placental blood before drug administration and in serum or plasma and urine on days 1 and 28, and 12 months CGA. TAF will be obtained on similar days if the infant is still intubated to evaluate the effects of a single IT dose of rhCC10 on native CC10 expression in the lungs. Total protein, TH2 cytokines, IL-6, and cellular infiltrates will also be evaluated in TAF samples, to the extent permitted by the volume of patient samples collected.

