5.3 Randomization

As previously described, two dose levels will be evaluated against the placebo in two consecutive cohorts. The first cohort will randomize patients to receive either 1.5 mg/kg or placebo. The second cohort will randomize patients to receive either 5 mg/kg or placebo. Each cohort will randomize 44 infants to either placebo or drug treatment. The overall design is 2:1:1; 44 (placebo):22 (1.5 mg/kg):22 (5mg/kg). The randomization scheme was developed and is maintained by StudyTrax, a secured electronic data capture platform that is compliant with 21 CFR-11 and HIPAA. A randomization ID is generated when a subject is randomized using the format TMC-001, BWH-002, and

so on (i.e. 3 letter site designation and three numbers designating the sequence in which the patient was enrolled). The randomization scheme uses the permuted block randomization method, with stratification by site and by gestational age group (divided into 24-27 wks CGA and 27-29 wks CGA), with block sizes 2,2,4. For Cohort 1, treatment groups are: Placebo and 1.5 mg/kg. When Cohort 1 is completed, Cohort 2 treatment groups will be: Placebo and 5.0 mg/kg. Cohort is also listed as a Stratification factor so that when Cohort 2 starts, any open blocks from the first cohort will not be filled. The Cohort is automatically set to 1 at the start of the study. Once Cohort 1 is done and Cohort 2 starts, that will change. Each site's pharmacy will receive authorization to access the patient randomization assignment via the Internet on StudyTrax.

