Power Analysis: A total of 88 preterm infants will be randomized to placebo, lower dose, or higher dose rhCC10 with an allocation ratio of 2:1:1. The primary analysis will be the comparison of placebo versus both rhCC10 dose groups combined. The prior trial demonstrated that the two doses are likely to yield similar results. Two doses will be used for the purpose of extending the safety profile for each individual dose, as that safety data may facilitate the choice of dose for a future Phase III confirmatory study. For SAEs or AEs with background rates of 5%, 10%, or 15%, the sample size of 22 in either dosing group will provide a probability of observing it of 68%, 90%, and 97%, respectively. The proposed trial is powered for the comparison of the two doses combined versus placebo for the composite endpoint of death or development of CRM. Secondarily, the study will yield effect size estimates for each individual dose versus placebo. Our assumptions regarding the comparison of placebo versus rhCC10 are based on the previous study with 7 placebo, 8 lower dose, and 7 higher dose infants (one infant in each of the rhCC10 treatment groups died). It is important to address the combined endpoint of death or re-admission to the hospital for respiratory problems. In the previous study, one loss-to-follow-up occurred in each of the three experimental groups and one death occurred in each of the rhCC10 groups. At 6 months, 3 of the 6 infants on placebo with follow-up were re-admitted to the hospital for respiratory problems and none of the 11 subjects treated with either rhCC10 dose with follow-up data were re-hospitalized. A realistic and conservative assumption for the 3 lost-to-follow-up babies is that they all either died or had respiratory disease. Then the proportions with disease or death on placebo and rhCC10 are assumed to have been 0.57 and 0.27. If the proportions in the proposed study are similar, with 44 subjects on placebo and 44 subjects in the two dose groups combined, power will be 82% with $\alpha=0.05$. nQuery Advisor version 6 was used.

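### The plan describes a three-group comparison from one 2:1:1 randomisation, but the doses run in consecutive cohorts, so 1.5 v 5 mg/kg is not randomised and is confounded with enrolment period

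*Combined protocol and SAP*

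**What the plan says.** Section 4 sets out three groups (44 placebo, 22 at 1.5 mg/kg, 22 at 5 mg/kg) and does not mention cohorts. It says "A total of 88 patients will be enrolled in three treatment groups in which high and low dose rhCC10 will be compared to placebo", and then "Complete results of the study should allow direct comparison of three groups".

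Section 8.5 says: "A total of 88 preterm infants will be randomized to placebo, lower dose, or higher dose rhCC10 with an allocation ratio of 2:1:1". It names a primary contrast (both doses combined v placebo) and secondary effect estimates for each dose v placebo. Of the two doses it adds "that safety data may facilitate the choice of dose for a future Phase III confirmatory study".

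Section 5.3 gives the mechanism, which is sequential: "two dose levels will be evaluated against the placebo in two consecutive cohorts". Only one dose is available at a time. On the opening stage it states: "The first cohort will randomize patients to receive either 1.5 mg/kg or placebo". On the next stage it states: "When Cohort 1 is completed, Cohort 2 treatment groups will be: Placebo and 5.0 mg/kg". Each cohort has 44 infants, and 2:1:1 appears there as the overall design. Cohort is a stratification factor in the randomisation.

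No analysis in 8.5 names cohort. The primary test is a 2 x 2 chi-square, and the logistic model names treatment, centre and their interaction. Chi-square or Fisher tests are prescribed for between-group comparisons in general, without saying which pairs of groups are meant.

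**The concern.** Under 5.3 no infant can be allocated between 1.5 and 5 mg/kg. A low v high comparison therefore also compares two enrolment periods, with any change in care, case mix or respiratory season included. A reader of Sections 4 and 8.5 alone would take it to be protected by randomisation.

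This matters because 8.5 foresees that dose-level safety data may help choose a dose for the next trial, and its general testing rule would permit a crude test between the doses. The documents themselves give one reason to expect risk to vary over time: Section 2.6 notes that necrotising enterocolitis (NEC) occurs in clusters, and Section 7.3 makes confirmed NEC a serious adverse event. A cluster during one cohort would look like a dose effect.

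The planned dose v placebo estimates are exposed too. The plan does not say that the placebo infants must be concurrent, and half of the 44 are non-concurrent for either dose.

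**Working it through.** **Inputs.** From 8.5: event proportions 0.57 (placebo) and 0.27 (rhCC10), 44 v 44, two-sided α = 0.05. From 5.3 and Section 4: 22 drug and 22 placebo infants per cohort. Drift between cohorts is my assumption, because the documents give none.

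**1. The plan's own figure.** Two-proportion normal approximation, pooled variance, no continuity correction, 44 v 44, 0.57 v 0.27: power 82.5%. The stated 82% reproduces.

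**2. Effect of drift on each contrast.** Suppose the doses are equally effective (true difference from placebo −0.30) and the event rate falls by *d* in all arms from Cohort 1 to Cohort 2.

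- Combined doses v all placebo: (0.27 + 0.27 − *d*)/2 − (0.57 + 0.57 − *d*)/2 = −0.30 for every *d*. The primary contrast is not biased, because allocation is 1:1 within each cohort.
- Crude 5 v 1.5 mg/kg: (0.27 − *d*) − 0.27 = −*d*. All of the drift appears as a dose difference.
- Each dose v all 44 placebo: biased by *d*/2, in opposite directions. At *d* = 0.10, pooled placebo is 0.52, so low dose shows 0.27 − 0.52 = −0.25 and high dose 0.17 − 0.52 = −0.35.
- Each dose v its own 22 placebo: −0.30 for both.

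Exact rejection rate of a nominal 5% chi-square on the crude 22 v 22 dose contrast, doses truly equal:

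| *d* | 0 | 0.05 | 0.10 | 0.15 | 0.20 |
|---|---|---|---|---|---|
| Rejects | 4.9% | 6.7% | 12.5% | 24.3% | 44.5% |

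**3. The same with a constant odds ratio.** OR = (0.57/0.43)/(0.27/0.73) = 3.58. If placebo drifts from 0.57 to 0.47, the treated rate in Cohort 2 is 0.198; if to 0.40, it is 0.157. The crude dose rates are then 0.27 v 0.20 or 0.27 v 0.16, and the crude test rejects in about 9% or 15% of trials.

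**4. Precision of the dose contrast at the plan's rates.** Per-arm variances: 0.27 × 0.73/22 = 0.00896 and 0.57 × 0.43/22 = 0.01114.

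- Crude risk difference: 1.96 × √(2 × 0.00896) = 0.26.
- Through each cohort's placebo: 1.96 × √(2 × 0.00896 + 2 × 0.01114) = 0.39.
- Crude log odds ratio: SE = √(2/(22 × 0.27 × 0.73)) = 0.679; factor exp(1.96 × 0.679) = 3.8.
- Ratio of the two within-cohort odds ratios: SE = √(2 × 0.416) = 0.912, where 0.416 = 1/(22 × 0.57 × 0.43) + 1/(22 × 0.27 × 0.73); factor exp(1.96 × 0.912) = 6.0.

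**5. The scale matters.** In the scenarios of step 3 the doses have equal odds ratios, yet the difference of risk differences is not zero: (0.198 − 0.47) − (0.27 − 0.57) = +2.8 points, and (0.157 − 0.40) − (0.27 − 0.57) = +5.7 points. A contrast through placebo must therefore state its scale.

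**6. Precision of each dose v placebo.** With 22 concurrent placebo infants the 95% half-width is 1.96 × √(0.00896 + 0.01114) = 0.28 and power is 52.3%. With all 44 pooled these are 1.96 × √(0.00896 + 0.01114/2) = 0.24 and 64.4%.

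**The case against.** The strongest reply is that the plan names no 1.5 v 5 mg/kg test. Section 4 also says that the doses are compared with placebo, its sentence on three groups may only summarise that, and Section 8 is headed exploratory. Section 8.5 expects the doses to perform alike, and it quantifies dose-level safety only as the chance of seeing an event in 22 infants. This stands as a reason not to overstate the point. It does not rescue the sentence, because a direct comparison of three groups includes low v high.

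Next, 2:1:1 is correct as a total, and 5.3 says so. That also stands: the fault in 8.5 is that it describes how the total is reached as one randomisation.

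Third, the drift is assumed, and a 7- to 11-point bias (step 3) is small beside a ±26-point interval. The assumption is conceded. The 44.5% rejection rate needs a 20-point fall and should not be taken as typical. The comparison of ±26 with ±39 needs no drift assumption.

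Fourth, 5.3 says imbalances in birth weight or gestational age will be taken into account, and 8.5 looks for baseline covariates. This covers measured case mix, but not changes in care, season or infection clusters.

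A reader might infer that the consecutive cohorts undermine the whole efficacy comparison. The documents do not support that: step 2 shows the combined contrast unchanged for every *d*. Nor do they support saying that neither dose can be compared with placebo under randomisation, since each has 22 concurrent randomised controls.

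**Conclusion.** The point holds as a mismatch between sections and a gap in the analysis rules. The design in 5.3 does not provide the direct three-group comparison stated in Section 4, and 8.5 describes a randomisation that does not take place in that form. Dose is fully confounded with enrolment period.

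A crude dose contrast takes on all of any between-cohort drift, and a dose estimate against pooled placebo takes on half. A contrast through concurrent placebo avoids the drift if the drug effect is constant on the chosen scale, at about ±39 rather than ±26 points, or a factor of 6.0 rather than 3.8 on the odds-ratio scale. These widths rest on the plan's 0.57 and 0.27 with 22 per arm. Every bias and rejection figure rests on an assumed drift. It would go too far to say that a wrong dose choice will follow: the plan says only that the safety data may help, and gives no rule for using them.

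**What to change.** - Reword Section 4 and 8.5 to match 5.3: two consecutive 1:1 randomisations that total 2:1:1.
- State that any 1.5 v 5 mg/kg comparison is non-randomised and descriptive, and exclude that pair from the between-group significance tests.
- Estimate each dose v placebo against the 22 placebo infants of its own cohort, or fit a model that includes cohort, which is already a randomisation stratum.
- If a dose contrast is reported to support dose choice, make it through each cohort's placebo (for example a treatment-by-cohort term on the odds-ratio scale), with a 95% CI and the scale stated. Which outcomes to report it for is the sponsor's decision; with 22 per arm, requiring it for every type of serious adverse event is not necessary.

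The cost is protocol and SAP wording, with no change to enrolment, dosing or sample size. The intervals become wider: the dose contrast as given in the verdict, and each dose v placebo about ±28 rather than ±24 points if its own 22 placebo infants are used in place of all 44.
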